10.4. Management of Potential Infusion-related Adverse Events During Ravulizumab Administration

Intravenous and infusion-related reactions are a potential risk with the use of monoclonal antibodies; these reactions can be nonimmune or immune mediated (eg, hypersensitivity reactions). Signs and symptoms may include headache, fever, facial flushing, pruritus, myalgia, nausea, chest tightness, dyspnea, vomiting, erythema, abdominal discomfort, diaphoresis, shivers, hypertension, lightheadedness, hypotension, palpitations, and somnolence. Signs and symptoms of hypersensitivity or allergic reactions may include hives, swollen face, eyelids, lips, or tongue, or trouble with breathing.

All administration-, IV-, and infusion-related reactions will be reported to the Investigator and qualified designee. The Investigator and qualified designee are responsible for detecting, documenting, and recording events that meet the definition of AE or SAE and remain responsible for following up events that are serious, considered related to the study drug, or study procedures; or that caused the participant to discontinue ravulizumab (Section 7).

Definitions and procedures for recording, evaluating, follow-up, and reporting AEs and SAEs are outlined in Section 10.3.

Participants who experience a reaction during the administration of ravulizumab should be treated according to institutional guidelines.

Participants who experience a severe reaction during administration of ravulizumab resulting in discontinuation of ravulizumab should undergo all scheduled safety, PK, and PD evaluations required by the protocol. Alexion must be notified within 24 hours of any infusion-related reaction requiring interruption or discontinuation of ravulizumab. All AEs that may indicate an infusion-related response will be graded according to CTCAE v5.0 or higher.

If anaphylaxis occurs according to the criteria listed in Table 14, then administration of subcutaneous epinephrine (1/1000, 0.3 mL to 0.5 mL, or equivalent) should be considered. In the case of bronchospasm, treatment with an inhaled beta agonist also should be considered. Participants administered an antihistamine for the treatment or prevention of an infusion-related reaction should be given appropriate warnings about drowsiness and impairment of driving ability before being discharged from the center.

Table 14: Clinical Criteria for Diagnosing Anaphylaxis

Anaphylaxis is highly likely when any 1 of the following 3 criteria is fulfilled:

• Acute onset of an illness (minutes to several hours) with involvement of the skin, mucosal tissue, or both (eg, generalized hives, pruritus or flushing, swollen lips-tongue-uvula), and at least 1 of the following:
◦ Respiratory compromise (eg, dyspnea, wheeze-bronchospasm, stridor, reduced peak expiratory flow, hypoxemia)◦ Reduced blood pressure or associated symptoms of end-organ dysfunction (eg, hypotonia [collapse], syncope, incontinence)

• Two or more of the following that occur rapidly after exposure to a likely allergen for that participant (minutes to several hours):
◦ Involvement of the skin-mucosal tissue (eg, generalized hives, itch-flush, swollen lips/tongue/uvula)◦ Respiratory compromise (eg, dyspnea, wheeze/bronchospasm, stridor, reduced peak expiratory flow, hypoxemia)◦ Reduced blood pressure or associated symptoms (eg, hypotonia [collapse], syncope, incontinence)◦ Persistent gastrointestinal symptoms (eg, crampy abdominal pain, vomiting)

• Reduced blood pressure after exposure to known allergen for that participant (minutes to several hours):
◦ Systolic blood pressure of less than 90 mmHg or greater than 30% decrease from that participant's baseline

Source: [Sampson, 2006](#)

10.5. Medication Error, Drug Abuse, and Drug Misuse

Medication Error

For the purposes of this clinical study a medication error is an unintended failure or mistake in the treatment process for a study intervention that either causes harm to the participant or has the potential to cause harm to the participant.

Any events of medication error, with or without associated AEs, are to be captured and forwarded to Alexion Global Patient Safety via email or facsimile ([contact] or [contact]) using the Alexion Clinical Study Medication Error Report Form.

A medication error is not lack of efficacy of the study intervention, but rather a human or process related failure while the intervention is under the control of the study site staff or participant.

Medication error includes situations where an error:

- Occurred
- Was identified and intercepted before the participant received the drug
- Did not occur, but circumstances were recognized that could have led to an error

Examples of events to be reported in clinical studies as medication errors:

- Drug name confusion
- Dispensing error, eg, medication prepared incorrectly, even if it was not actually given to the participant
- Drug not administered as indicated, eg, wrong route or wrong site of administration
- Drug not taken as indicated, eg, tablet dissolved in water when it should be taken as a solid tablet
- Drug not stored as instructed, eg, kept in the refrigerator when it should be at room temperature
- Wrong participant received the medication (excluding IRT/Randomization and Trial Supply Management [RTSM] errors)
- Wrong drug administered to participant (excluding IRT/RTSM errors)

Examples of events that **do not** require reporting as medication errors in clinical studies:

- Errors related to or resulting from IRT/RTSM - including those which led to one of the above listed events that would otherwise have been a medication error
- Participant accidentally missed drug dose(s), eg, forgot to take medication
- Accidental overdose (will be captured as an overdose [refer to Section 8.6 for information on overdose])
- Participant failed to return unused medication or empty packaging

Medication errors are not regarded as AEs but AEs may occur as a consequence of the medication error.

Drug Abuse

For the purpose of this study, drug abuse is defined as the persistent or sporadic intentional, nontherapeutic excessive use of study intervention for a perceived reward or desired nontherapeutic effect.

Any events of drug abuse, with or without associated AEs, are to be captured and forwarded to Alexion Global Patient Safety via email or facsimile ([contact] or [contact]) using the Alexion Clinical Study Drug Misuse or Drug Abuse Report Form. This form should be used both if the drug abuse happened in a study participant or if the drug abuse involves a person not enrolled in the study (such as a relative of the study participant).

Examples of drug abuse include but are not limited to:

- The drug is used with the intent of getting a perceived reward (by the study participant or a person not enrolled in the study)
- The drug in the form of a tablet is crushed and injected or snorted with the intent of getting high

Drug Misuse

Drug misuse is the intentional and inappropriate use of study intervention for medicinal purposes outside of the authorized product information, or for unauthorized study intervention, outside the

intended use as specified in the protocol, including deliberate administration of the product by the wrong route.

Events of drug misuse, with or without associated AEs, are to be captured and forwarded to Alexion Global Patient Safety via email or facsimile ([contact] or [contact]) using the Alexion Clinical Study Drug Misuse or Drug Abuse Report Form. This form should be used both if the drug misuse happened in a study participant or if the drug misuse involves a person not enrolled in the study (such as a relative of the study participant).

Examples of drug misuse include but are not limited to:

- The drug is used with the intention to cause an effect in another person
- The drug is sold to other people for recreational purposes
- The drug is used to facilitate assault in another person
- The drug is deliberately administered by the wrong route
- The drug is split in half because it is easier to swallow, when it is stated in the protocol that it must be swallowed whole
- Only half the dose is taken because the study participant feels that he/she is feeling better when not taking the whole dose
- Someone who is not enrolled in the study intentionally takes the drug

10.6. Contraceptive Guidance and Collection of Pregnancy Information

10.6.1. Definitions

Woman of Childbearing Potential

A woman is considered fertile following menarche and until becoming post-menopausal unless permanently sterile (see below).

If fertility is unclear (eg, amenorrhea in adolescents or athletes) and a menstrual cycle cannot be confirmed before first dose of study drug, additional evaluation should be considered.

Women in the following categories are not considered WOCBPs.

1. Premenarchal
2. Premenopausal female with one of the following:
 - Documented hysterectomy
 - Documented bilateral salpingectomy
 - Documented bilateral oophorectomy
 - For individuals with permanent infertility due to an alternate medical cause other than the above, (eg, Mullerian agenesis, androgen insensitivity), Investigator discretion should be applied to determining study entry.
 - Note: Documentation can come from the site personnel's: review of the participant's medical records, medical examination, or medical history interview.
3. Postmenopausal female
 - A postmenopausal state is defined as no menses for 12 months without an alternative medical cause.
 - A high follicle stimulating hormone (FSH) level in the postmenopausal range may be used to confirm a postmenopausal state in women not using hormonal contraception or hormonal replacement therapy (HRT). However, in the absence of 12 months of amenorrhea, confirmation with more than 1 FSH measurement may be required.
 - Females on HRT and whose menopausal status is in doubt will be required to use one of the non-estrogen hormonal highly effective contraception methods if they wish to continue their HRT during the study. Otherwise, they must discontinue HRT to allow confirmation of postmenopausal status before study enrollment.

10.6.2. Contraception Guidance

10.6.2.1. Guidance for Female Participants

Female participants of non-childbearing potential are exempt from contraception requirements. Non-childbearing potential for female participants is defined as any of the following:

1. Prior to first menses

2. Postmenopausal, as documented by amenorrhea for at least 1 year prior to the Day 1 Visit. Confirmatory FSH serum levels consistent with postmenopausal status may be obtained by the Investigator at Screening. In the absence of 12 months of amenorrhea, multiple elevated FSH levels will be required. The reason for not obtaining an FSH should be documented by the Investigator at the time of Screening
3. Permanent sterilization at least 6 weeks prior to the Day 1 Visit
4. Hysteroscopic sterilization
5. Bilateral tubal ligation or bilateral salpingectomy
6. Hysterectomy
7. Bilateral oophorectomy

Female participants of child-bearing potential must use a highly effective method of contraception, including at least 1 of the following until at least 8 months after the final dose of study drug:

1. Intrauterine device in place for at least 6 weeks prior to first dose.
2. Progestogen-only hormonal contraception (either oral, injectable, or implantable) for at least 6 weeks prior to first dose.
3. Intrauterine progestogen releasing system for at least 6 weeks prior to first dose.
4. Bilateral tubal occlusion for at least 6 weeks prior to first dose.
5. Combined (estrogen- and progestogen-containing) hormonal contraception (either oral, intravaginal, or transdermal) for at least 6 weeks prior to first dose.
6. Surgical sterilization of the male partner (medical assessment of azoospermia is required if vasectomy was performed within 6 months prior to first dose).
7. Sexual abstinence for female participants:
 - Sexual abstinence is considered a highly effective method only if defined as refraining from heterosexual intercourse. In this study, abstinence is only acceptable if consistent with the participant's preferred and usual lifestyle. Abstinent female participants who wish to initiate a highly effective method of contraception during the study must refrain from heterosexual intercourse for at least 8 months after the final dose of study drug.
 - Periodic abstinence (eg, calendar, symptothermal, or post-ovulation methods) is not considered a highly effective method of contraception for female participants.

Other methods of contraception that are not considered highly effective for female participants:

1. Barrier methods, such as male or female condoms, diaphragm, or cervical cap, used alone or in combination, are not acceptable.
2. Spermicides or spermicidal sponges, used alone or in combination with barrier methods, are not acceptable.

Withdrawal (coitus interruptus) is not acceptable.

Lactational amenorrhea is not acceptable.

Female participants must not donate ova from the Day 1 visit until 8 months after the final dose of study drug.

10.6.2.2. Guidance for Male Participants

Contraception is the responsibility of the heterosexually active male participants, regardless of his female partner's method of contraception.

Male participants who have had a vasectomy > 6 months prior to first dose must use a condom during heterosexual intercourse. Male participants who have had a vasectomy < 6 months prior to first dose must use a condom and spermicide during heterosexual intercourse.

Male participants who have not had a vasectomy must use a condom and spermicide during heterosexual intercourse 8 months after their final dose of study drug.

10.6.2.2.1. Sexual Abstinence for Male Participants

Sexual abstinence is considered a highly effective method only if defined as refraining from heterosexual intercourse. In this study, abstinence is only acceptable if consistent with the participants' s preferred and usual lifestyle. Abstinent male participants who become heterosexually active must use a condom and spermicide during intercourse.

Periodic abstinence (eg, calendar, symptothermal, or post-ovulation methods for a female partner) is not considered a highly effective method of contraception for male participants.

Male participants must not donate sperm from the Day 1 visit until 8 months after their final dose of study drug.

10.6.3. Collection of Pregnancy Information

Pregnancy data will be collected during this study for all female participants and female spouses/partners of male participants from the signing of the ICF until 8 weeks after last dose of the study drug is administered. Any female participant who becomes pregnant while participating in the study will be discontinued from the study drug. Exposure during pregnancy (also referred to as exposure in utero) can be the result of either maternal exposure or transmission of study drug via semen following paternal exposure. If a female participant or a male participant's female partner becomes pregnant during the conduct of this study, the Investigator must submit the "Pregnancy Reporting and Outcome/Breastfeeding" form to Alexion GDS via facsimile or email. When the outcome of the pregnancy becomes known, the form should be updated and submitted to Alexion GDS. If additional follow-up is required, the Investigator will be requested to provide the information.

Exposure of an infant to study drug during breastfeeding must also be reported (via the "Pregnancy Reporting and Outcome Form/Breastfeeding") and any AEs experienced by the infant must be reported to Alexion GDS or designee via email or facsimile.

Pregnancy is not regarded as an AE unless there is a suspicion that the study drug may have interfered with the effectiveness of a contraceptive medication. However, complications of pregnancy and abnormal outcomes of pregnancy are AEs and may meet the criteria for an SAE

(eg, ectopic pregnancy, spontaneous abortion, intrauterine fetal demise, neonatal death, or congenital anomaly). Elective abortions without complications should not be reported as AEs.

Any female participant who becomes pregnant while participating in the study will be discontinued from study drug.

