Serious infection	
Apart from the predictable risk of infection with Neisseria species, which is well known and directly related to the mechanism of action of ravulizumab, the mechanism that may lead to other serious infections in participants treated with ravulizumab remains unclear. Since the relevance of serious infection with ravulizumab therapy has not been confirmed in clinical studies, this remains a potential risk. In this study, because participants with LN will be immunosuppressed due to concomitant steroid and MMF use, they will be at increased risk of serious infections due to the immunosuppressant use.
	
All participants will be required to be vaccinated for Hib and S pneumonia, according to current national/local guidelines, in addition to N meningitidis. Healthcare professionals and participants should have increased awareness about the potential risk of serious infection. Monitoring for signs and symptoms of serious infections will be conducted as part of the safety assessments for this study.

Immunogenicity	
Treatment with any therapeutic protein has the potential to induce an immune response. Potential clinical consequences may include hypersensitivity, anaphylaxis or related type of reactions or loss of efficacy.
 
Fewer than 1% of participants in the ravulizumab Phase 2 and 3 studies had positive ADA samples.
	
Monitoring for hypersensitivity and serious infusion-related reactions will be conducted as part of safety assessments for this study (Section 10.4).
 
Infusion should be stopped in the event of any intervention-related severe adverse events like systemic hypersensitivity or anaphylaxis.
 
In case of suspected SAEs of hypersensitivity or anaphylaxis, additional ADA samples may be collected during or in proximity of the event.

Pregnancy exposure/lactation	
No studies of ravulizumab have been conducted in pregnant or breastfeeding women. There are no data available on excretion of ravulizumab in breast milk.
	
Pregnant or nursing female participants will be excluded from the clinical study. Women and men enrolled in the study, and their spouses/partners, must use a highly effective or acceptable method of contraception for a period of 8 months following the final dose of study intervention. Breastfeeding should be discontinued during treatment and up to 8 months after treatment with ravulizumab (Section 10.6).

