8.3.6. Pregnancy

Pregnancy testing must be performed on all women of childbearing potential (WOCBPs) at protocol-specified time points in the SoA (Section 1.3). Pregnancy tests (urine or serum) may also be performed at any time during the study at the Investigator's discretion.

A negative pregnancy test is required for WOCBPs before study drug administration.

- Any female participant who becomes pregnant while participating in the study will be discontinued from the study drug.
- If a pregnancy is reported, the Investigator must immediately inform Alexion within 24 hours of awareness of the pregnancy and follow the procedures outlined in Section 10.6.3.
- Details of all pregnancies in female participants and female spouses/partners of male participants will be recorded and the pregnancy followed to term and Alexion notified regarding the outcome, even if the participant discontinues the study drug or withdraws from the study. The corresponding infant must be followed-up with for 3 months postpartum.
- Pregnancy is not considered as an AE unless there is a suspicion that the study drug may have interfered with the effectiveness of a contraceptive medication. However, complications of pregnancy and abnormal outcomes of pregnancy are AEs and may meet the criteria for an SAE (eg, ectopic pregnancy, spontaneous abortion, intrauterine fetal demise, neonatal death, or congenital anomaly) (Section 10.3.2). Elective abortions without complications should not be reported as AEs.

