8.13. Post-treatment Follow-up Period

During the 36-week Post-treatment Follow-up Period, participants will continue to receive standard of care and will be monitored for clinical events of interest and kidney function.

All participants will be followed for safety until 8 weeks after the participant's last dose of study drug to collect information on concomitant medications, nonpharmacological therapies and procedures, and AEs. The final safety evaluation for participants in the LN will occur at the Week 50 Visit and participants in the IgAN cohort will have a Follow-up Phone Call performed at Week 52.

Participants are not required to come into the clinic for the Post-treatment Follow-up Period visits. At each Post-treatment Follow-up Visit through Week 86, the information described below will be documented in the participant's CRF for the 12-week period since the previous study visit.

For participants in both cohorts, the following laboratory results will be documented:

- Record the UPCR results from the participant's most recent standard of care testing conducted by local laboratory. Spot urine studies may be used; a morning void is preferred.
- Record serum creatinine results from the participant's most recent standard of care testing conducted by local laboratory.

For participants in the LN cohort, information will include, but is not limited to:

- In the Investigator's opinion, did the patient experience a renal flare or extrarenal flare
- Documentation of any changes in immunosuppression therapy (intensified, new agent, or change in dose)
- Progression of kidney disease including dialysis and kidney transplant

For participants in the IgAN cohort, information will include, but is not limited to:

- Progression of kidney disease including dialysis and kidney transplant
- Documentation of any changes in immunosuppressive therapy (new agent or change in dose)
- Documentation of any changes in alternative therapy (new agent or change in dose)

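### Protocol Section 10.6.3 ends pregnancy data collection 8 weeks after the last dose, contradicting the protocol's wider reporting rules and its 8-month precautions, and no pregnancy question is scheduled after Week 50

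*Protocol*

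**What the plan says.** **The explicit cutoff.** Protocol Section 10.6.3 opens by collecting pregnancy data, for female participants and for partners of male participants, "from the signing of the ICF until 8 weeks after last dose of the study drug is administered".

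**The wider rules.** Section 8.3.6 states: "Details of all pregnancies in female participants and female spouses/partners of male participants will be recorded and the pregnancy followed to term". It applies this even after the participant stops study drug or leaves the study. Further on, Section 10.6.3 requires the pregnancy form for a pregnancy arising at any time while the study is being conducted. Sections 10.6.3.1 (partners) and 10.6.3.2 (female participants) ask for information on any pregnancy that begins during participation. None of these carries an 8-week limit, and participation runs to Week 86.

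**The 8-month precautions.** Table 6 in Section 2.3.1 says that men and women in the study, and their partners, "must use a highly effective or acceptable method of contraception for a period of 8 months following the final dose of study intervention", and that "Breastfeeding should be discontinued during treatment and up to 8 months after treatment with ravulizumab". Section 10.6.2.1 states: "Female participants must not donate ova from the Day 1 visit until 8 months after the final dose of study drug". Section 10.6.2.2.1 states: "Male participants must not donate sperm from the Day 1 visit until 8 months after their final dose of study drug". The Participant Safety Card (Section 8.3.1) is also carried for 8 months.

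**The schedule.** Tables 3 and 4 place the last pregnancy test at Week 50 or early discontinuation. Table 5, covering Weeks 52 to 86, has no pregnancy row. Footnote a of Table 13 nevertheless calls for a serum test at the End of Study Visit, which Section 4.5 places at Week 86.

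**The concern.** Table 6 records that ravulizumab has not been studied in pregnant or breastfeeding women, so each pregnancy during or soon after treatment is safety information worth having. The protocol asks participants to avoid conception for 8 months after the last dose, but the one sentence that sets a date for collecting pregnancy data stops at 8 weeks.

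Two things follow. Sites may apply different rules: one stops at Week 50 or 52 on the strength of 10.6.3, while another continues to Week 86 under 8.3.6. Even a site that takes the wider view has no scheduled prompt to ask, so it learns of a pregnancy only if the participant volunteers it.

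**Working it through.** This is day arithmetic on the schedule; no power or alpha input is involved.

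**Inputs**
- Last scheduled dose: LN Day 295, Week 42 (Table 3); IgAN Day 309, Week 44 (Table 4).
- Collection cutoff: 8 weeks = 56 days (Section 10.6.3).
- Precaution period: 8 months (Table 6; Sections 8.3.1 and 10.6.2).
- End of study: Day 603, Week 86 (Table 5).
- Assumption: a month is 30.44 days, so 8 months = 243.5 days = 34.8 weeks. The range shown uses 28 to 30.44 days.
- Study week = (day − 1) / 7.

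**Reproducing the protocol's own figures.** Section 8.13 puts the 8-week point at Week 50 (LN) and Week 52 (IgAN).
- LN: 295 + 56 = Day 351; (351 − 1)/7 = Week 50.
- IgAN: 309 + 56 = Day 365; (365 − 1)/7 = Week 52.
- Study length: 26 + 24 + 36 = 86 weeks.

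All agree.

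**Where 8 months ends**
- LN: 295 + 243.5 = Day 538.5; (538.5 − 1)/7 = Week 76.8.
- IgAN: 309 + 243.5 = Day 552.5; (552.5 − 1)/7 = Week 78.8.

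Both precede Week 86.

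**Share of the 8 months beyond the cutoff**
- 34.8 − 8 = 26.8 weeks; 26.8 / 34.8 = 77%.
- With 28-day months: 32 − 8 = 24 weeks; 24 / 32 = 75%.

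**The same calculation under the wider rules.** If 8.3.6, 10.6.3.1 and 10.6.3.2 govern, a participant still in the study is covered to Week 86 and the share outside is 0%. The choice of sentence moves the result from 0% to 77%.

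**What the schedule supports.** The weeks beyond the cutoff are about 50 to 76.8 (LN) and 52 to 78.8 (IgAN). Weeks 62 and 74 fall inside both spans. Week 86 comes about 9 weeks (LN: 86 − 76.8 = 9.2) or 7 weeks (IgAN: 86 − 78.8 = 7.2) after 8 months, so a question then that looks back to the last dose would span the whole period.

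**The case against.** The strongest reply is that the data are already required. Four provisions, one of them inside 10.6.3, ask for any pregnancy during the study, and participation lasts to Week 86. Pregnancy complications and abnormal outcomes are also adverse events, which Section 8.4.1 collects to Week 86 from participants who do not stop drug early, and Table 5 has an adverse-event phone visit at Week 86. A precaution period and a data-collection period need not be equal, and 8 weeks is the protocol's usual post-dose safety interval.

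Much of this stands. A reader might infer that most of an exposure window is simply not covered. The documents do not support that: they never call 8 months an exposure window (that is an inference from the precaution rules), and the wider provisions do cover participants still in the study. A reader might also infer that mycophenolate in the LN cohort enlarges the gap. The protocol requires it only to Week 50, which is where the LN gap begins, and the 8-month rules are tied to study drug, so the point does not rest on it.

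The reply does not remove the contradiction. The 10.6.3 sentence is the only one with a dated cutoff and is the natural one for a site to apply. The adverse-event route is partial: Section 8.3.6 says pregnancy is not an adverse event unless contraceptive interference is suspected, and uncomplicated elective abortions are not reported as such. Normal outcomes, and with them the denominator, would be missed. That route is itself described inconsistently, since Section 8.13 says "The final safety evaluation for participants in the LN will occur at the Week 50 Visit".

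**Conclusion.** The point holds as an internal contradiction together with missing scheduled ascertainment. The protocol gives two end dates for pregnancy data, and Table 5 provides no test or question after Week 50 by which the later one could be met. If a site follows the explicit cutoff, about 27 of the 35 weeks after the last dose (75% to 77%, depending on the length taken for a month) go uncollected.

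That figure is a share of weeks, not of pregnancies; the documents give no pregnancy rate from which to project a number lost. It assumes the last dose was given as scheduled at Week 42 or 44. It should not be read as data certainly lost, because a site following 8.3.6 would lose none that came to its notice.

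Nor are all participants still followed during the gap. Section 4.1 follows those who withdraw for 8 weeks after the last dose, and asks those who stop drug early but stay in the study to attend visits to Week 50. Section 8.4.1 ends adverse-event collection at 8 weeks for those who stop drug early.

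The matter concerns safety data only. The primary analysis, sample size and power are not touched. It is worth correcting because it is plain and inexpensive to correct.

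**What to change.** 1. In Section 10.6.3, replace the cutoff so that collection runs to the end of study participation and at least 8 months after the last dose, and word 8.3.6, 10.6.3.1 and 10.6.3.2 to match. Merely exchanging 8 weeks for 8 months would end collection near Week 77 or 79 and still conflict with the two subsections that run to the end of participation.
2. Add a pregnancy row to Table 5: a question, looking back to the last dose, at the existing Week 86 phone visit, and at Weeks 62 and 74 where the participant is contacted. The qualification is needed because Table 5 marks phone visits for adverse events and medications only at Week 52 (IgAN) and Week 86; at Weeks 62 and 74 it lists recording of local laboratory results and monitoring for flare or progression, and Section 8.13 requires no clinic attendance.
3. Reconcile footnote a of Table 13 with Table 5 on testing at the End of Study Visit.

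**Cost.** For participants who complete the study, this means a reworded sentence, one table row and one case report form question. Participants who withdraw or stop study drug early would need one added contact near 8 months after their last dose, where they still consent to it. No dose, treatment or contraception rule changes, and the efficacy analysis is unaffected.
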